6.4.1.3. Nonresponder Imputation

The nonresponder imputation (NRI) method will be used to handle missing data relative to the supportive estimand for categorical endpoints (composite). Patients who receive rescue medication (per Protocol Section 6.3), or discontinue treatment, will be set to non-response subsequent to this time through Week 16. Intermittent missing values will also be set to non-response.

The nonresponder imputation (NRI) method imputes missing values as non-responders and can be justified based on the composite strategy (ICH E9R1) for handling intercurrent events. In this strategy patients are defined as responders only if they meet the clinical requirements for response at the predefined time AND they remain on the assigned study treatment (i.e. not using rescue medications and not having missing values due to other reasons). Failing either criteria by definition makes them nonresponders.

Randomized patients without at least 1 postbaseline observation will also be defined as nonresponders for all visits for the NRI analysis.

6.4.1.4. Last Observation Carried Forward (LOCF)

In this analysis, the values subsequent to rescue medication use (per Protocol Section 6.3) or treatment discontinuation will be made missing. All missing values will be imputed using LOCF. Baseline value will be used for imputation if there is no postbaseline observation.

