## 7.2. Baseline Visit (Day 1) Induction Period

- Administer the DLQI/CDLQI and EQ-5D
- Administer the PROMIS (Patient-Reported Outcomes Measurement Information System): Anxiety and Depression measures
- Collect the ACQ-5 assessment for patients with comorbid asthma
- Update medical history/review of systems and concomitant medication and procedure/therapy information
- Complete the following assessments: IGA, BSA, EASI and SCORAD
- Review compliance report on the eDiary and confirm moisturizer use
- Measure vital signs
- Draw a pre-dose blood sample for PK and anti-drug antibody (ADA) testing
- Conduct urine pregnancy test (WOCBP only)
- Re-assess and confirm patient eligibility (Inclusion/Exclusion criteria)
- Randomize the patient, receive kit assignment, and administer study drug
- Remind patient to record the following: Pruritus and Sleep-Loss (daily), and POEM (weekly)

Sites collecting photos will also:

- Obtain written informed consent for collecting photos
- Select a target lesion and obtain a photograph

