## 7.3. Week 2 ( $\pm$ 3 Days)

- Complete the following assessments: IGA, BSA and EASI
- Review and record AEs and update concomitant medication and procedure/therapy information
- Review compliance report on the eDiary, confirm moisturizer use and remind patient to record the following: Pruritus and Sleep-Loss (daily), and POEM (weekly)

- Measure vital signs
- Administer study drug

Sites collecting photos will also:

- Obtain photographs of the target lesion

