For variables that are not collected at each postbaseline visit, data may exist at visits where the variable was not scheduled to be collected. In these situations, data from the early discontinuation visit that do not correspond to the planned collection schedule will be excluded from the MMRM analysis (Andersen and Millen 2013). Also for by-visit summaries/displays such as boxplots, the weeks when data was not scheduled to be collected may not be displayed. However, unscheduled assessments within any defined study period will still be used in the shift analyses, and for imputing values for the change from baseline to last observation carried forward (LOCF) endpoint analyses.

The Kaplan-Meier (KM) product limit method maybe used to estimate the survival for time to event analyses. The log-rank test stratified by the stratification factors mentioned in Section 6.3 will be reported. A Kaplan-Meier plot of the time to event by treatment group may be provided.

Unless specified otherwise, Fisher's exact test will be used for adverse events (AEs) and other categorical safety measures. Odds ratios will be created with lebrikizumab treatment as the numerator, and placebo as the denominator. Continuous vital sign and laboratory values will be analyzed by an ANCOVA with treatment and baseline value in the model.

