6.2.1.3. Supportive Estimand for Continuous Endpoints (Hypothetical)

The supportive estimand for continuous endpoints is a hypothetical estimand representing the supportive clinical question of interest: what is the difference between treatment conditions in the target patient population, in means after 16 weeks if rescue medication was not available and all patients adhered to the treatment?

The supportive estimand is described by the following attributes:

- A. Population: defined through appropriate I/E criteria to reflect the targeted patient population for approval
- B. Endpoint: apply to continuous endpoints
- C. How to account for intercurrent events (ICEs)
 - a. For subjects who require any use of rescue medication or discontinue treatment prior to week 16, a hypothetical strategy will be used to estimate what the treatment effect would have been if rescue medication was not available and all subjects adhered to the treatment. Therefore, hypothetical strategy is used for these types of ICEs.
- D. Population-level summary: difference in means between treatment conditions

Analytical details on how missing data including those as a result of intercurrent events will be handled for Induction Period can be found in Section 6.4.1. Detailed analyses relative to estimands including analysis type, method and imputation, population, time point, and treatment comparisons for efficacy/health outcomes analyses can be found in Section 6.11.

The following table (Table KGAB.6.3) summarizes the analytical strategies that will be conducted on the intercurrent events for the three estimands.

Table KGAB.6.3. Description of Primary and Supportive Estimands for Induction Period

Estimand	Analysis Strategy for Intercurrent Events			Missing Data Imputation Method
	Rescue Medication	Treatment Discontinuation		
		Due to lack of efficacy	Due to any other reasons	
Primary Estimand (Hybrid)	Composite: Set to baseline	Composite: Set to baseline	Hypothetical: Set to missing	Primary analysis: MCMC-MI Sensitivity analysis: tipping point analysis
Supportive Estimand for Categorical Endpoints (Composite)	Composite: Set to non-responder	Composite: Set to non-responder	Composite: Set to non-responder	NRI
Supportive Estimand for Continuous Endpoints (Hypothetical)	Hypothetical: Set to missing	Hypothetical: Set to missing	Hypothetical: Set to missing	MMRM, LOCF

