6.4.1. Handling of Dropouts or Missing Data for Induction Period

For efficacy analysis relative to the primary estimand, the primary method of handling missing data including those as a result of intercurrent events will be based on Markov Chain Monte Carlo Multiple Imputation (MCMC-MI). The description of MCMC-MI method can be found in Section 6.4.1.1. Tipping point analysis as described in Section 6.4.1.2 will serve as the sensitivity analysis for the primary analysis.

For efficacy analysis relative to the supportive estimand for categorical endpoints, missing data including those as a result of intercurrent events will be imputed as non-responder. The description of non-responder imputation (NRI) can be found in Section 6.4.1.3.

For efficacy analysis relative to the supportive estimand for continuous endpoints collected only once post-baseline, missing data including those as a result of intercurrent events will be imputed using Last Observation Carried Forward (LOCF). The description of LOCF can be found in Section 6.4.1.4.

For efficacy analysis relative to the supportive estimand for continuous endpoints collected multiple times post-baseline, a Mixed Model for Repeated Measures (MMRM) will be performed without explicit imputation. The description of MMRM can be found in Section 6.4.1.5.

Table KGAB.6.6 describes the planned imputation methods for efficacy and health outcome endpoints for Induction Period.

Table KGAB.6.6. Imputation Techniques for Various Variables During Induction Period

Type of Endpoints	Efficacy and Health Outcome Endpoints	Estimand (Analysis strategy for Intercurrent Events)	Missing Data Imputation Method (Analysis Method)
Categorical	IGA, EASI, Pruritus NRS, sleep loss and DLQI related categorical endpoints at pre-specified timepoints	Primary Estimand (Hybrid)	MCMC-MI, Tipping point analysis (CMH)
		Supportive Estimand (Composite)	NRI (CMH)
	Remaining categorical endpoints	Supportive Estimand (Composite)	NRI (CMH)
Continuous	EASI percent change, Pruritus NRS percent change, Sleep loss change from baseline, DLQI change from baseline	Primary Estimand (Hybrid)	MCMC-MI (ANCOVA)
		Supportive Estimand (Hypothetical)	No imputation (MMRM)
	Remaining continuous endpoints collected at multiple post-baseline timepoints including BSA, POEM and CDLQI	Supportive Estimand (Hypothetical)	No imputation (MMRM)
	Remaining continuous endpoints collected only once post-baseline	Supportive Estimand (Hypothetical)	LOCF (ANCOVA)

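### For continuous Week 16 SCORAD, EQ-5D, PROMIS and ACQ-5, the LOCF rule scores rescued patients, and discontinued patients whose early-termination value is not used, as zero change under an estimand labelled hypothetical

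*SAP*

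**What the plan says.** SAP 6.2.1.3 defines the supportive estimand for continuous endpoints as the treatment difference "in means after 16 weeks if rescue medication was not available and all patients adhered to the treatment". Table KGAB.6.12 assigns this estimand, with ANCOVA and LOCF, to the Week 16 change scores of SCORAD, EQ-5D (VAS and both index scores), PROMIS and ACQ-5. No primary-estimand or MMRM row exists for them.

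SAP 6.4.1 gives the method: "continuous endpoints collected only once post-baseline, missing data including those as a result of intercurrent events will be imputed using Last Observation Carried Forward (LOCF"). SAP 6.4.1.4 adds two rules: "In this analysis, the values subsequent to rescue medication use (per Protocol Section 6.3) or treatment discontinuation will be made missing", and "Baseline value will be used for imputation if there is no postbaseline observation".

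SAP 6.1.2 says that "unscheduled assessments within any defined study period will still be used in the shift analyses". The same sentence goes on to name LOCF endpoint analyses as a second use of such assessments.

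Table KGAB.6.3 describes the same handling, in the primary estimand's row, as a composite strategy: values after rescue or a lack-of-efficacy discontinuation are set to baseline. In the hypothetical estimand's row the strategy is to set them to missing.

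**The concern.** A hypothetical estimand asks what a patient would have scored at Week 16 without rescue and on full treatment. Assigning the baseline score answers a different question: it counts the event as no benefit. If the method delivers the second under the label of the first, the reported difference does not estimate its stated target. This LOCF analysis is the only comparative analysis planned for these continuous change scores. BSA, POEM and CDLQI sit under the same estimand but are analysed by MMRM under missing at random, so results sharing one label would not be comparable.

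**Working it through.** **Step 1. What there is to carry.** At baseline Protocol 7.2 lists "Complete the following assessments: IGA, BSA, EASI and SCORAD", together with EQ-5D, PROMIS and ACQ-5. At Week 2 Protocol 7.3 lists only "Complete the following assessments: IGA, BSA and EASI", and none of the four instruments is scheduled from Week 2 to Week 14. All four return at Week 16 (Protocol 7.10; Appendix 1, Table 6). An unscheduled visit for a flare calls for IGA, BSA and EASI only (Protocol 7.22). The early-termination visit collects all four (Protocol 7.20). It is required for patients who permanently stop drug, except those on systemic rescue, who stay on the visit schedule to Week 16 (Protocol 8.7.2 and 6.3).

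**Step 2. Apply SAP 6.4.1.4.**

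| Patient | Values on file | Carried to Week 16 | Change scored |
|---|---|---|---|
| No event | Baseline, Week 16 | Week 16 kept | Observed |
| Rescued, attends Week 16 | Baseline, post-rescue Week 16 | Baseline (Week 16 deleted) | Zero |
| Discontinued, early-termination value treated as after discontinuation | Baseline, early termination | Baseline (early termination deleted) | Zero |
| Discontinued, early-termination value kept through SAP 6.1.2 | Baseline, early termination | Early termination | Early termination minus baseline |

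The second and third rows are the set-to-baseline assignment that Table KGAB.6.3 calls composite. The fourth row holds an early score fixed, which is still not the Week 16 score under full adherence. The SAP does not say whether row three or row four applies.

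**Step 3. Size, for SCORAD percentage change.** The plan states no figure to reproduce. All inputs below are assumptions except the sample size (about 400 at 2:1, so 267 and 133).

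- Improvement in patients without an event: 55 points on lebrikizumab, 30 on placebo
- Event rate d: 10-20% on lebrikizumab, 20-30% on placebo
- Improvement h that event patients would have had (forgone under baseline carry): 25-45 on lebrikizumab, 5-15 on placebo
- SD 30

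With m the improvement in patients without an event, the arm mean under the stated estimand is (1-d)m + dh. Under baseline carry it is (1-d)m, so each arm is understated by dh:

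- Lebrikizumab: 0.10 x 25 = 2.5 to 0.20 x 45 = 9.0
- Placebo: 0.20 x 5 = 1.0 to 0.30 x 15 = 4.5

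Understatement of the difference is dh on lebrikizumab minus dh on placebo:

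- Lowest: 0.10 x 25 - 0.30 x 15 = -2.0, that is, 2.0 overstated
- Highest: 0.20 x 45 - 0.20 x 5 = 8.0 understated

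True difference:

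- Lowest: (0.80 x 55 + 0.20 x 25) - (0.80 x 30 + 0.20 x 15) = 49 - 27 = 22
- Highest: (0.90 x 55 + 0.10 x 45) - (0.70 x 30 + 0.30 x 5) = 54 - 22.5 = 31.5

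Difference under baseline carry:

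- Lowest: 0.80 x 55 - 0.80 x 30 = 20
- Highest: 0.90 x 55 - 0.70 x 30 = 28.5

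Standard error: 30 x sqrt(1/267 + 1/133) = 3.2. The shift therefore runs from 0.6 standard errors overstated to 2.5 understated, while the smallest carried difference is 20/3.2, about 6 standard errors.

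**The case against.** A reader might infer that every discontinued patient is scored as zero change. The documents do not establish this. The early-termination visit supplies all four instruments, and SAP 6.1.2 can be read as feeding that value into LOCF. A reader might also infer that 6.1.2 and 6.4.1.4 flatly contradict each other. They can be read as a general rule and a method-specific one. What is left is an ambiguity: the SAP does not say whether an early-termination value counts as subsequent to discontinuation. Nor do the documents support a bias of known direction, because the sign reverses within one modest set of assumptions.

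The consequence is also limited. These are other secondary endpoints, absent from both multiplicity lists in SAP 6.6, and primary and major secondary endpoints use multiple imputation. SCORAD75, SCORAD90 and the EQ-5D domain responses have openly composite non-responder analyses at Week 16. Imputing from other instruments goes beyond the SAP's existing imputation model, which uses only the relevant baseline and post-baseline values. Relabelling alone would also remove the mismatch.

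All of this stands, and it sets the scope and weight of the point. It does not touch the rescued patients, for whom the mismatch is plain, or the need for one early-termination rule.

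**Conclusion.** The concern holds in this form: for the continuous change scores of these four instruments, the method and the stated estimand do not match. That is certain for rescued patients. For discontinued patients it holds whichever way the early-termination value is read, but the score is zero change only if that value is not used. The mismatch follows from the documents alone. Its size does not: no rescue rate, dropout rate or SCORAD effect is given, and the range from 2.0 points overstated to 8.0 understated rests wholly on the assumed inputs and on baseline being carried for every event patient. On those inputs the estimate can be off by more than two standard errors, but the test result is unlikely to change. The point should be fixed; it does not threaten the trial's main conclusions.

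**What to change.** In Tables KGAB.6.3, KGAB.6.6 and KGAB.6.12, for continuous induction endpoints with one post-baseline visit, replace LOCF by multiple imputation under missing at random, separately by arm. Use the endpoint's own baseline plus pre-event values of measures collected more often: EASI and IGA for SCORAD, and POEM with the itch and sleep diary for EQ-5D and PROMIS. ACQ-5 has no such companion measure, so an ANCOVA on values unaffected by rescue or discontinuation, adjusted for baseline, would serve.

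Alternatively, keep the baseline carry and relabel the analysis as a composite, set-to-baseline estimand.

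In either case, state one rule in SAP 6.1.2 and 6.4.1.4 for whether an early-termination value is used.

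The cost is slightly more programming on data already collected, and reliance on missing at random, which the SAP's MMRM rows for this estimand already assume. SAP version 4 was approved after the sponsor's study team was unblinded to induction treatment, so an induction change made at this version should be documented as such. One transparent route is to relabel the LOCF analysis and add the missing-at-random analysis as supplementary.

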6.4.1.5. Mixed-effects Model for Repeated Measures

Mixed Model for Repeated Measures analyses will be performed on continuous endpoints to mitigate the impact of missing data. This approach assumes missing observations are missing-at-random (missingness is related to observed data) and borrows information from patients in the same treatment arm taking into account both the missingness of data through the correlation of the repeated measurements.

When MMRM is used, the model includes treatment, baseline value, visit, the interaction of the baseline value-by-visit, the interaction of treatment-by-visit, and the stratification factors mentioned in Section 6.3 as fixed factors. The covariance structure to model the within-patient errors will be unstructured.

6.4.2. Handling of Dropouts or Missing Data for Maintenance Period

For maintenance efficacy analysis relative to the maintenance primary estimand, the method of handling missing data including those as a result of intercurrent events will be Markov Chain Monte Carlo Multiple Imputation (MCMC-MI). The description of maintenance MCMC-MI method can be found in Section 6.4.2.1.

MCMC-MI will also be used to handle missing data relative to the maintenance supportive estimand (Hybrid) as described in Section 6.4.2.1.

For efficacy analysis relative to the maintenance supportive estimand for categorical endpoints (Composite), missing data including those as a result of intercurrent events will be imputed as non-responder. The description of maintenance non-responder imputation (NRI) can be found in Section 6.4.2.2.

For efficacy analysis relative to the maintenance supportive estimand for continuous endpoints (Hypothetical), missing data including those as a result of intercurrent events will be imputed using Last Observation Carried Forward (LOCF). The description of maintenance LOCF can be found in Section 6.4.2.3.

Table KGAB.6.9 describes the planned imputation methods for efficacy and health outcome endpoints for Maintenance Period.

Table KGAB.6.9. Imputation Techniques for Various Variables During Maintenance Period

Type of Endpoints	Efficacy and Health Outcome Endpoints	Estimand (Analysis strategy for Intercurrent Events)	Missing Data Imputation Method (Analysis Method)
Categorical	IGA, EASI, and Pruritus NRS related categorical endpoints at pre-specified timepoints	Maintenance Primary Estimand (Hybrid)	MCMC-MI (CMH)
		Maintenance Supportive Estimand (Hybrid)	MCMC-MI (CMH)
		Maintenance Supportive Estimand (Composite)	NRI (CMH)
	Remaining categorical endpoints	Maintenance Supportive Estimand (Composite)	NRI (CMH)
Continuous	EASI percent change, Pruritus NRS percent change	Maintenance Primary Estimand (Hybrid)	MCMC-MI (ANCOVA)
		Maintenance Supportive Estimand (Hybrid)	MCMC-MI (ANCOVA)
		Maintenance Supportive Estimand (Hypothetical)	LOCF (ANCOVA)
	Remaining continuous endpoints	Maintenance Supportive Estimand (Hypothetical)	LOCF (ANCOVA)

Abbreviations: ANCOVA = analysis of covariance; CMH = Cochran-Mantel-Haenszel; EASI = Eczema Area and Severity Index; IGA = Investigator's Global Assessment for AD; LOCF = last observation carried forward; MCMC-MI = Markov chain Monte Carlo multiple imputation; MMRM = mixed-model repeated measures; NRI = Nonresponder Imputation; NRS = Numeric Rating Scale.

6.4.2.1. Maintenance Period MCMC-MI

The MCMC-MI will be used to handle missing data relative to the maintenance primary estimand (Hybrid) and maintenance supportive estimand (Hybrid) for both binary and continuous endpoints. Imputation will be conducted within each treatment group independently so the pattern of missing observations in one treatment group cannot influence missing value imputation in another. The SAS PROC MI with MCMC option will be used to conduct the MCMC-MI. The imputation model will include the relevant baseline and post-baseline.

For each imputation process, 25 datasets with imputations will be calculated. The initial seed values are given in [Table KGAB.6.7](#). Each complete data set will be analyzed with the specified analysis. The results from these analyses will be combined into a single inference using SAS PROC MIANALYZE.

Cochran-Mantel-Haenszel (CMH) test statistic will be transformed using the Wilson-Hilferty transformation and then standardized (Ratitch 2013) prior to combining them using SAS PROC

MIANALYZE. Details of combining estimates and test statistics for categorical endpoints with multiple imputation can be found in [Appendix 2](#).

The imputation and analysis will be conducted on Maintenance Primary Population only.

The derivation of binary responses related to EASI, IGA and Pruritus NRS for Maintenance Period will follow the derivation for Induction Period.

Table KGAB.6.10. Seed Values for MCMC-MI for Maintenance Period

Analysis	Seed values Lebrikizumab 250 mg Q2W/Q4W/ Placebo
IGA	12345
EASI	12346
Pruritus NRS score	12347

Abbreviations: EASI = Eczema Area and Severity Index score; IGA = Investigator's Global Assessment for AD; MCMC = Markov chain Monte Carlo multiple imputation; NRS = Numeric Rating Scale; Q2W = every 2 weeks; Q4W=every 4 weeks.

6.4.2.2. Maintenance Period NRI

The nonresponder imputation (NRI) method will be used to handle missing data relative to the maintenance supportive estimand for categorical endpoints (composite). Patients who receive rescue medication (per Protocol Section 6.3), discontinue treatment, or transfer to escape arm will be set to non-response subsequent to this time through Week 52 Intermittent missing values will also be set to non-response.

Re-randomized patients without at least 1 postbaseline observation will also be defined as nonresponders for all visits for the NRI analysis.

6.4.2.3. Maintenance Period LOCF

Maintenance LOCF will be used to handle missing data relative to maintenance supportive estimands for continuous endpoints (Hypothetical). In this analysis, the values subsequent to rescue medication use (per Protocol Section 6.3), treatment discontinuation or transfer to escape arm will be made missing. All missing values will be imputed using LOCF. Baseline value will be used for imputation if there is no postbaseline observation.

